6.4 Summary of known and potential risks and benefits

See chapter 13 for the complete text.

There are no major risks associated with this study. The subjects will use their usual kind of diabetes therapy, in which only the type of insulin is adjusted for thirty days. The most prominent risk is potential altered effectiveness of Lyumjev compared to the currently used insulin, which could lead to hypo- and hyperglycemia, but high and low glucose values will be indicated by alarms given by the AP system.

The individual benefit for the participating patients could be an improved glycemic control during the study.

The burden of the study is relatively low. The participants have to visit the CRC at most 2 times. Besides, the only additional burden for participants is to keep a Wi-Fi access point with them during both study periods.

6.5 Description and justification of route of administration and dosage

Lyumjev will be administered by the AP system in the same way Humalog (the reference insulin) is administered. This administration is performed by a pump which can administer doses in the order of 0.25 units. One unit corresponds to 0.01 ml which equals 0.01 mg of insulin using a concentration of 1.0 mg/ml (as used during this study). One dose administration is 0.25 units, corresponding to 0.0025 mg insulin. No maximum total dose per day is defined.

6.6 Dosages, dosage modifications and method of administration

The dosage of Lyumjev that will be administered by the Inreda AP system is determined by the control algorithm and depends on the patient's current sensor glucose and the rate of change of the glucose level.

Moreover, maintenance doses are administered by the Inreda AP system to prevent infusion set occlusion. This maintenance dose equals 0.25 units per hour, in case no insulin determined by the control algorithm is administered for 1 hour.

Lyumjev should be stored in the refrigerator (2-8 °C) before use. To protect the insulin from light, it should be stored in the original package. After first use, it should not be stored above 30 °C.

6.7 Preparation and labelling of Investigational Medicinal Product

Both the investigational Lyumjev insulin and the control Humalog insulin will be delivered by the pharmacy in cartridges of 3 ml, applicable for the Inreda AP system.

6.8 Drug accountability

The investigator will maintain adequate records showing dispensing, return, or other disposition of the Lyumjev insulin including the date, quantity, batch or code number, and identification of participants who received Lyumjev insulin. The investigator will not supply the drug to any person except sub-investigators, designated trial personnel, and participants in this trial.

All used and unused Lyumjev insulin will be stored until study closure and final reconciliation have been performed to ensure compliance.

7. NON-INVESTIGATIONAL PRODUCT

Not applicable.

7.1 Name and description of non-investigational product(s)

Not applicable.

7.2 Summary of findings from non-clinical studies

Not applicable.

7.3 Summary of findings from clinical studies

Not applicable.

7.4 Summary of known and potential risks and benefits

Not applicable.

7.5 Description and justification of route of administration and dosage

Not applicable.

7.6 Dosages, dosage modifications and method of administration

Not applicable.

7.7 Preparation and labelling of Non Investigational Medicinal Product

Not applicable.

7.8 Drug accountability

Not applicable.

8. METHODS

8.1 Study parameters/endpoints

8.1.1 Main study parameter/endpoint

The main study parameter is the proportion of time spent above range (>10 mmol/l).

8.1.2 Secondary study parameters/endpoints (if applicable)

The safety parameters are:

- Side effects of Lyumjev

The pharmacodynamic parameters are:

- Proportion of time spent in euglycemia (3.9-10.0 mmol/l);
- Proportion of time spent in hypoglycemia (<3.9 mmol/l);
- Proportion of time spent in level 2 hypoglycemia (<3.0 mmol/l);
- Proportion of time spent in level 2 hyperglycemia (>13.9 mmol/l);
- Mean/median glucose value;
- Glycemic variability expressed as coefficient of variation and interquartile range (IQR).

The pharmacodynamic parameters and the main endpoint will be calculated for the whole study period and for daytime (06:00–00:00 h) and nighttime (00:00–06:00 h) separately.

AP-related parameters are:

- Daily administered dosage of glucagon;
- Daily administered dosage of insulin;
- The percentage of time that the closed loop algorithm is active.

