6.3 Summary of findings from clinical studies

There were four studies conducted to compare the pharmacodynamics of Lyumjev with Humalog [5]–[8]. The results of these studies demonstrate that Lyumjev insulin is non-inferior to Humalog in terms of effectiveness and may improve postprandial glucose control. Interestingly, improved postprandial control is seen only after breakfast, but not after lunch or dinner. Nonetheless, this is promising for AP therapy. Moreover, large studies do not give rise to alarm with regard to side-effects, as similar rates of adverse events are observed in most studies. However, an increase in infusion site reactions was observed and requires attention. So far, large outpatient studies did not include patients on pump therapy. To date, the reported studies have not tested Lyumjev insulin in closed-loop systems. Closed-loop systems are generally able to maintain glycemic control, but postprandial peaks are the final hurdle to achieve normoglycemia in patients using these devices. Using Lyumjev in the AP would potentially further improve glycemic control.

No clinical studies were performed with Lyumjev in combination with the AP system.

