8.3 Study procedures

The study starts with informing the patients about the study. If patients want to participate the informed consent form will be signed first and thereafter the patients will be screened, which can be performed online or in the CRC. The study will be performed at home and subjects can live according to their own daily routine.

At the start of the first study period the subject will receive the insulin cartridges for the first study period. After the first 30 days, there will be a washout period of 8 days where subjects will use Humalog. After the wash-out period the subjects will receive the second insulin formulation according to randomization. The same procedure as written above will be repeated. During the study conduct there will be four additional visits by the investigator: at the start and end of both the intervention and control period.

If adverse events occur during the study, the subject has to contact the investigator. If desired, an unscheduled visit could take place. If a device deficiency occurs during the study, the subject has to contact the investigator only if this is insulin-related. If there are other technical problems, the patient should follow the regular treatment protocol and contact the customer service of Inreda Diabetic B.V.

During both study periods subjects are asked to keep a Wi-Fi access point with them so researchers can assess the data if necessary. No active real-time monitoring will be performed during the study, the standard monitoring protocol will be complied. This includes monthly portal assessments and assessments at the request of the customer service.

At the start of the study the self-learning algorithm status (on or off) will not be changed. This means that the self-learning algorithm is turned on or off depending on the setting prior to the study.

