9.2 AEs, SAEs and SUSARs

9.2.1 Adverse events (AEs)

Adverse events are defined as any undesirable experience occurring to a subject during the study, whether or not considered related to the investigational product. All adverse events reported spontaneously by the subject or observed by the investigator or his staff will be recorded.

If adverse events occur during the study, the subject has to contact the investigator. If desired, an unscheduled visit could take place. If device deficiencies occur during the study, the subject has to contact the investigator only if it is insulin-related. If there are other technical problems, the patient should follow the regular treatment protocol and contact the customer service of Inreda Diabetic.

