5.1.2 Artificial Pancreas dataset

The AP sends data to the AP Portal system every 10 minutes. The following data will be collected in the AP Portal system:

- AP, transmitters and mobile access point identification;
- Sensor glucose concentration;
- Sensor glucose slope;
- Sensor state;
- Insulin and glucagon administrations;
- Physical activity parameter measured by accelerometers;
- Control algorithm state;
- Events registered by the AP (e.g., low and high glucose alarm, calibrations, infusion set occlusion and replacements, sensor replacements).

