5.3.2 Secondary study parameters

The secondary safety and performance parameters will be compared between the two types of insulin using dependent t-tests or Wilcoxon signed rank tests. T-tests or Wilcoxon signed rank tests for:

- Time in hypoglycemia. It is hypothesized that the time below range is not higher for Lyumjev when compared to Humalog. A one tailed test shall be performed with:
 $H_0: \mu_{\text{Lyumjev}} \leq \mu_{\text{Humalog}}$
 $H_1: \mu_{\text{Lyumjev}} > \mu_{\text{Humalog}}$
- Time in euglycemia. It is hypothesized that the time in range is not lower for Lyumjev when compared to Humalog. A one tailed test shall be performed with

Revision	D02	Document number:	SAP
	Document title:	FAST-1	
	Status:	APPROVED	
	TPL 013.D02	This document is uncontrolled when printed	

$H_0: \mu_{\text{Lyumjev}} \geq \mu_{\text{Humalog}}$,

$H_1: \mu_{\text{Lyumjev}} < \mu_{\text{Humalog}}$

- Mean or median glucose. It is hypothesized that the mean or median glucose is not higher for Lyumjev when compared to Humalog. A one tailed test shall be performed with:

$H_0: \mu_{\text{Lyumjev}} \leq \mu_{\text{Humalog}}$

$H_1: \mu_{\text{Lyumjev}} > \mu_{\text{Humalog}}$

- Glycemic variability expressed as coefficient of variation and interquartile range. It is hypothesized that the glycemic variability is not higher for Lyumjev when compared to Humalog. A one tailed test shall be performed with:

$H_0: \mu_{\text{Lyumjev}} \leq \mu_{\text{Humalog}}$

$H_1: \mu_{\text{Lyumjev}} > \mu_{\text{Humalog}}$

The pharmacodynamic parameters and the main endpoint will be calculated for the whole study period and for daytime (06:00–00:00 h) and nighttime (00:00–06:00h) separately.

Other endpoints are the AP-related parameters:

- Daily administered dosage of glucagon;
- Daily administered dosage of insulin;
- The percentage of time that the closed loop algorithm is active.

No statistical testing will be performed on these parameters.

6 Missing data

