8.1 Description of the deviations from the SAP

1. Standard deviation (SD) of the glucose value

- a. Rationale: SD of the glucose value was included as variable because of its added value to indicate glycemic variability.
- b. Detailed description: the SD of the glucose value was added as parameter considering it is a commonly used parameter besides the coefficient of variation and interquartile range of the glucose value to indicate glycemic variability. The SD was calculated for day time, night time and the combination. No data were affected by the addition of this parameter.
- c. Date of decision: May 1, 2023.
- d. People involved in the decision (with signature): [name], [name] and [name].

2. Time below range (TBR) and time above range (TAR)

- a. Rationale: level 1 and level 2 for the TBR and TAR were included in order to report all the important glycemic metrics, following the International Consensus guidelines.
- b. Detailed description: according to the SAP, only the TBR and TAR in total should be calculated (not as separate levels). In addition to the total TBR and TAR, also level 1 and 2 of the TBR and TAR were calculated. These are essential parameters to indicate glycemic control, following the International guidelines on how to report glycemic metrics (Battelino *et al*, Lancet Diabetes Endocrinol (2023)). These metrics were calculated for day time, night time and the combination. These additional parameters had no effect on the data.

Revision	D02	Document number:	SAP
	Document title:	FAST-1	
	Status:	APPROVED	
	TPL 013.D02	This document is uncontrolled when printed	

- c. Date of decision: May 1, 2023.
- d. People involved in decision (with signature): [name], [name] and [name].

3. Exclusion of AP data acquired for five participants

a. Rationale:

A critical procedural error was discovered in the process of data analysis, which led to invalidity of a part of the FCL data. FCL data from the Lyumjev-Humalog sequence (n=5) had to be excluded. Other data from this sequence could still be included (e.g., adverse events). To mention that all FCL data from the Humalog-Lyumjev sequence (n=7) were included.

b. Details on deviation:

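### The one listed safety parameter names Lyumjev only, and the SAP specifies no adverse-event or infusion-site comparison between the insulins, although events are recorded on both

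*Protocol*

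**What the plan says.** **Objective and parameter.** Protocol section 2 puts safety first among the secondary objectives. The pharmacodynamic and device-related objectives are worded as differences between the two insulins; the safety objective is not. Protocol 8.1.2 gives safety one parameter, "Side effects of Lyumjev", without an event definition, time window or Humalog counterpart.

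**Risk flagged.** Protocol 6.3 reports that "an increase in infusion site reactions was observed and requires attention" and adds that the large outpatient studies had no pump users. Protocol 13.1 names local pain relative to Humalog as a safety issue.

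**Collection.** Protocol 9.2.1 defines an adverse event as "any undesirable experience occurring to a subject during the study, whether or not considered related to the investigational product", and states: "All adverse events reported spontaneously by the subject or observed by the investigator or his staff will be recorded". Protocol 8.3 says "there will be four additional visits by the investigator: at the start and end of both the intervention and control period", but describes no site inspection or question. SAP section 4 states that there is no blinding.

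**Analysis.** Protocol section 10 mentions an analysis of adverse events and device deficiencies that includes withdrawals, and leaves details to the SAP. SAP 5.3.2 opens with "The secondary safety and performance parameters will be compared between the two types of insulin", then lists time in hypoglycemia, time in euglycemia, mean or median glucose, and variability. SAP 5.1.2 shows that the device logs "infusion set occlusion and replacements".

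**After Deviation 3.** SAP 8.1 drops the closed-loop data of the five Lyumjev-first participants, but says: "Other data from this sequence could still be included (e.g., adverse events").

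**The concern.** The protocol raises a risk that is comparative by nature: more site reactions, and possibly more pain, than on Humalog. The parameter meant to cover it has no comparator. A team that follows 8.1.2 literally would report Lyumjev events alone, and a reader could not tell whether a given number is high for people wearing infusion sets every day.

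Ascertainment is passive and open-label. Participants know which insulin they are using, may report more on the new one, and may leave out minor site trouble that they regard as normal. Without a standard question, the wording and thoroughness of enquiry can differ between visits and centres.

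The stake grew after Deviation 3. The glycemic outcomes now rest on seven participants who all took Humalog first, so insulin and period cannot be separated. Adverse events are retained from both orders, so a within-participant description with both sequences represented is still possible there.

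**Working it through.** **1. What the plan links together.**

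| Element | Humalog covered? | Where |
|---|---|---|
| Flagged risk | Yes, as reference for pain | Protocol 6.3, 13.1 |
| Safety parameter | No | Protocol 8.1.2 |
| Adverse events recorded | Yes, whatever the relatedness | Protocol 9.2.1 |
| Adverse-event analysis foreseen | Not stated, no method | Protocol 10 |
| Tests for secondary parameters | Pharmacodynamic and device parameters only | Protocol 10.2 |
| Comparison of safety parameters | Announced; only glucose metrics listed | SAP 5.3.2 |

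The gap therefore lies in the parameter's wording and in the missing analysis, not in the scope of recording. Two details suggest an omission rather than a decision. SAP 5.3 refers descriptive analyses to a section 5.3.3 that is in neither the contents list nor the text. SAP section 6 has a missing-data remark on event counts, while no event-count parameter is defined.

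**2. The plan's own sample size.** Inputs from Protocol 4.4: means 12.8 and 9.675, both SDs 3.3, correlation 0.70.

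- SD of differences = √(3.3² + 3.3² − 2 × 0.70 × 3.3 × 3.3) = √6.534 = 2.556
- Standardised difference = 3.125 / 2.556 = 1.22
- Two-sided paired t-test at 0.05: power 0.893 with 9, 0.929 with 10

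The stated 10 is reproduced. It concerns time above range; the documents give no figure for safety.

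**3. What 12 participants can say about site reactions.** The documents state no reaction rate, so the risks below are assumptions shown over a range.

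- No affected participant among 12: one-sided 95% upper limit = 1 − 0.05^(1/12) = 0.22. The two-sided 95% interval reaches 1 − 0.025^(1/12) = 0.26.
- Chance of at least one affected participant, 1 − (1 − p)^12: 46% if p = 5%, 72% if p = 10%, 93% if p = 20%.
- Two-sided exact McNemar test at 0.05: five discordant participants, all one way, give 2 × 0.5⁵ = 0.0625; six give 2 × 0.5⁶ = 0.031. Fewer than six can never reach significance.
- Power of that test with n = 12, assuming independence within participant:

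| Assumed risk, Lyumjev v Humalog | Power |
|---|---|
| 20% v 5% | 1.1% |
| 30% v 5% | 7.3% |
| 40% v 5% | 22% |
| 50% v 5% | 45% |

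For 80% power, about 85 participants would be needed at 20% v 5% and about 45 at 30% v 5% (searched in steps of five). A formal test is out of reach under any wording; a table with intervals is the right target.

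**The case against.** The strongest reply is that little is lost. All adverse events count whatever their cause, so the Humalog periods are covered. Protocol 8.3 and 9.2.1 oblige participants to contact the investigator when an event occurs, and staff observation counts too. Protocol section 10 already foresees an adverse-event analysis. The risk that the protocol calls most prominent is altered glycemic effect, and SAP 5.3.2 does test time in hypoglycemia.

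Most of this stands, and it limits the point. Three stronger readings are tempting, and the documents do not support them:

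- *The trial collects an uncontrolled Lyumjev count and so cannot judge the site risk.* The recording rule contradicts the first half. As to the second, the number of participants is what prevents a firm judgement, and rewording would not change that.
- *A known share of reactions is lost, or wash-out time inflates Humalog exposure.* No capture rate is given, so the loss cannot be sized. Protocol section 3 keeps the wash-out apart from the two periods; the plan is merely silent on where wash-out events go.
- *The device log already answers the question.* Occlusions and set replacements do not measure pain or skin reaction, and replacements may be routine. Deviation 3 is titled as an exclusion of device data, and the text does not settle whether the event log is included. If it is, seven Humalog-first participants remain; if not, the other five used Humalog under Lyumjev settings.

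The reply leaves one thing unanswered: neither document says how events on the two insulins will be set against each other, and testing time in hypoglycemia says nothing about infusion sites.

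**Conclusion.** The point holds as a cheap improvement. A safety parameter naming one insulin does not match a risk stated relative to the other, and the SAP does not supply the adverse-event analysis that Protocol section 10 leaves to it. Collection covers both insulins, so a within-participant description is available from data already held.

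The gain is a readable comparison, not a test. With 12 participants, zero events would still be compatible with a risk of about 22% (one-sided 95% limit), and power against 20–30% v 5% is 1% to 7%. These power figures rest on assumed risks and independence within participant. The use of all 12 rests on the statement in Deviation 3 that adverse events remain usable. Glucose-related events in the second period of the five Lyumjev-first participants need a footnote, because they arose under settings meant for the other insulin.

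**What to change.** 1. **Protocol 8.1.2:** reword the parameter to side effects on each insulin.
2. **SAP 5.3.2:** add a descriptive table over the two 30-day periods. For any adverse event and for infusion-site events, count participants affected on both insulins, on Lyumjev only, on Humalog only and on neither, by insulin in use at onset. Include all 12 participants, give exact intervals and list wash-out events separately. Say explicitly that the five training days count here, since Protocol section 3 leaves training data out of the analysis.
3. **Interpretation:** state that 12 participants support description only, and quote the 22% limit for zero events.
4. **Visits:** ask one standard infusion-site question at the four existing visits; the start visits give a baseline and the end visits cover the period.
5. **Device log:** occlusions and unscheduled set replacements may be shown as supportive description, once the SAP states whether the event log falls under Deviation 3.

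The cost is a few lines of SAP text, one table and one question per visit. The downside is that asked-for reports raise event counts on both insulins and remain open-label.

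Deviation 3, decided in May 2023, was found during data analysis, so the question can no longer be asked in this trial. The table can still be produced, labelled post hoc as Protocol section 10 requires.

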8.1.3 Other study parameters (if applicable)

Other study parameters include: demographic characteristics, weight, length, HbA1c, relevant medical history and current medication use. Furthermore, occurrence of technical issues with the Inreda AP system will be recorded.

8.2 Randomisation, blinding and treatment allocation

The allocation sequence for the intervention and control arms will be generated by block randomization with an equal allocation ratio.

8.3 Study procedures

The study starts with informing the patients about the study. If patients want to participate the informed consent form will be signed first and thereafter the patients will be screened, which can be performed online or in the CRC. The study will be performed at home and subjects can live according to their own daily routine.

At the start of the first study period the subject will receive the insulin cartridges for the first study period. After the first 30 days, there will be a washout period of 8 days where subjects will use Humalog. After the wash-out period the subjects will receive the second insulin formulation according to randomization. The same procedure as written above will be repeated. During the study conduct there will be four additional visits by the investigator: at the start and end of both the intervention and control period.

If adverse events occur during the study, the subject has to contact the investigator. If desired, an unscheduled visit could take place. If a device deficiency occurs during the study, the subject has to contact the investigator only if this is insulin-related. If there are other technical problems, the patient should follow the regular treatment protocol and contact the customer service of Inreda Diabetic B.V.

During both study periods subjects are asked to keep a Wi-Fi access point with them so researchers can assess the data if necessary. No active real-time monitoring will be performed during the study, the standard monitoring protocol will be complied. This includes monthly portal assessments and assessments at the request of the customer service.

At the start of the study the self-learning algorithm status (on or off) will not be changed. This means that the self-learning algorithm is turned on or off depending on the setting prior to the study.

